13. PHARMACEUTICAL INFORMATION

Carfilzomib Description

Carfilzomib is a synthetic small molecule peptide bearing the chemical name (2S)-N-((S)-1-((S)-4-methyl-1-((R)-2-methyloxiran-2-yl)-1-oxopentan-2-ylcarbamoyl)-2-phenylethyl)-2-((S)-2-(2-morpholinoacetamido)-4-phenylbutanamido)-4-methylpentanamide. The molecular formula is C₄₀H₅₇N₅O₇ and the molecular weight is 719.91. It specifically functions as an inhibitor of the chymotrypsin-like activity of the 20S proteasome which leads to the accumulation of protein substrates within the cell and induction of apoptosis.

Formulation

Carfilzomib for Injection will be provided as a lyophilized powder which, when reconstituted, contains 2 mg/mL isotonic solution of carfilzomib Free Base in 10 mM sodium citrate buffer (pH 3.5) containing 10% (w/v) sulfobutylether- β -cyclodextrin (SBE- β -CD, Captisol[®]).

Availability

Carfilzomib is provided to UAB Cancer Center under a Collaborative Agreement with Onyx.

Agent Ordering

Carfilzomib may be requested from Onyx by the Principal Investigator (or their authorized designee) at each participating institution. The responsible investigator at each participating institution must be registered through an annual submission of FDA form 1572 (Statement of Investigator), Curriculum Vitae, Supplemental Investigator Data Form (IDF), and Financial Disclosure Form (FDF). If there are several participating investigators at one institution, carfilzomib should be ordered under the name of one lead investigator at that institution.

Storage

Lyophilized Carfilzomib for Injection must be stored at 2–8°C under the conditions outlined in the separate Pharmacy Manual, in a securely locked area to which access is limited to appropriate study personnel.

Accountability

Onyx, Inc. and the Investigator will maintain records of each shipment of investigational product. The records will document shipment dates, method of shipment, batch numbers, and quantity of vials contained in the shipment. Upon receipt of the investigational product, the designated recipient at the study site will inspect the shipment, verify the number and condition of the vials, and prepare an inventory or drug accountability record. Drug accountability records must be readily available for inspection by representatives of Onyx and by regulatory authorities. Empty and partially used vials should be accounted for and destroyed at the study site in accordance with the internal standard operating procedures. Drug destruction records must be readily available for inspection by representatives of Onyx and by regulatory authorities.

Only sites that cannot destroy unused drug on-site will be required to return their unused supply of investigational product.

14. **DATA REPORTING / REGULATORY CONSIDERATIONS**

Adverse event lists, guidelines, and instructions for AE reporting can be found in Section 7.0 (Adverse Events: List and Reporting Requirements). The CTNMO Coordinating Center Manager also ensures that the following are accomplished:

- Develop and implement plans for monitoring and auditing CTNMO site studies
- Provide initial protocol and consent documents to CTNMO sites
- Coordinate CTNMO site initiation visits / teleconferences
- Receive and evaluate documents from CTNMO sites and determine the need for further evaluation
- Submit required regulatory documentation to the UAB IRB
- Generate study-specific queries and develop resolutions
- Perform monitoring visits at CTNMO sites
- Provide for needed fiscal management including development of CTNMO site budgets and sub-contracts
- Provide for distribution of study-specific funds to CTNMO sites.

Data Reporting

Data collection and submission is the responsibility of the site Lead Investigator. Data collection forms are provided by the CTNMO Coordinating Center Manager. Each CTNMO site maintains a study-specific research data file (research chart) for study subjects enrolled into a study. The research chart includes completed CRFs and copies of all source documentation. Completed CRFs are reviewed, signed and dated by CTNMO site Lead Investigator. Any deviations from the study protocol are documented in the study subject's medical record and research chart. Missing data is documented in the research chart. Copies of the completed CRFs, other study-related documents, and source documents are faxed to the CTNMO Coordinating Center Manager on a monthly basis.

Multicenter guidelines and study monitoring

This protocol will adhere to the policies and requirements of Multicenter trial Guidelines. Each study subject is discussed at the CTNMO site's weekly Clinical Trials Monitoring

Committee meeting by the CTNMO site research nurses and Lead Investigator and is, in turn, presented at the next weekly CCC Clinical Trials Monitoring Committee meeting by the CTNMO Coordinating Center Manager. All questions and concerns regarding the conduct of a study at a CTNMO site are directed to the site Lead Investigator who consults with the CTNMO Director and / or the CTNMO Coordinating Center Manager when necessary. The P.I. (assisted by the CTNMO Coordinating Center Manager) is the primary contact for study-specific questions such as dose modifications, toxicities, and supportive care. The CTNMO Coordinating Center Manager is the primary contact for issues regarding patient registration, regulatory documents, completion of CRFs, data collection, and data submission.

Comprehensive monitoring of all CTNMO site studies (100% of patients) is conducted “off-site” at the CTNMO Coordinating Center using the CRFs and supporting source documents that are transmitted from the CTNMO site on a monthly basis. Following each monitoring exercise, queries and/or requests for additional documentation are generated by the CTNMO Coordinating Center Manager generally within 2 weeks of receipt of the CTNMO site documents. Subsequently, the CTNMO site reviews and responds to queries and implements the necessary corrective action(s). Within two weeks, the CTNMO site submits query responses and, if appropriate, a written summary of corrective actions to the CTNMO Coordinating Center Manager. When necessary, the CTNMO Coordinating Center Manager conducts “on-site” monitoring visits to provide staff education and to assist in implementing corrective action at the CTNMO site.

Informed Consent

Patients will receive a written and IRB approved current informed consent form. Patients will be provided with information regarding the trial and alternatives available for therapy. The risks and potential benefits will be provided.

Compliance with Laws and Regulations

The study will be conducted in accordance with U.S. Food and Drug Administration (FDA) and International Conference on Harmonization (ICH) Guidelines for Good Clinical Practice (GCP), the Declaration of Helsinki, Health Canada, any applicable local health authority, and Institutional Review Board (IRB) or Ethics Committee requirements.

This study must have the approval of a properly constituted IRB or Ethics Committee. Before the investigational drug is shipped to the Investigator, the Investigator or designee will provide Onyx with a copy of the IRB or Ethics Committee approval letter stating that the study protocol and any subsequent amendments and informed consent form have been reviewed and approved. The Investigator or designee will be responsible for obtaining annual IRB or Ethics Committee reapproval throughout the duration of the study. Copies of the Investigator’s annual report to the IRB or Ethics Committee and copies of the IRB or Ethics Committee continuance of approval must be provided to Onyx as follows:

Onyx Inc., Regulatory Department
[name],
[name]

The Investigator is also responsible for notifying their IRB or Ethics Committee of any significant adverse events that are serious and/or unexpected. Onyx will provide study sites with any expedited safety reports generated from any ongoing studies with carfilzomib, changes to the Investigator's Brochure, and any other safety information which changes the risk/benefit profile of carfilzomib during the conduct of the study, to allow him/her to fulfill his/her obligation for timely reporting to the IRB/ECs and other Investigators participating in the study. Upon completion of the trial, the Investigator must provide the IRB or Ethics Committee and Onyx with a summary of the trial's outcome.

Subject Confidentiality

Subject medical information obtained as part of this study is confidential, and must not be disclosed to third parties, except as noted below. The subject may request in writing that medical information be given to his/her personal physician. The Investigator/Institution will permit direct access to source data and documents by Onyx, its designee, the FDA and/or other applicable regulatory authority. The access may consist of trial-related monitoring, audits, IRB or Ethics Committee reviews, and FDA inspections.

Release of research results should preserve the privacy of medical information and must be carried out in accordance with Department of Health and Human Services Standards for Privacy of Individually Identifiable Health Information, 45 CFR 164.508.

APPENDIX A: Performance Status Criteria

ECOG Performance Status Scale		Karnofsky Performance Scale	
Grade	Descriptions	Percent	Description
0	Normal activity. Fully active, able to carry on all pre-disease performance without restriction.	100	Normal, no complaints, no evidence of disease.
		90	Able to carry on normal activity; minor signs or symptoms of disease.
1	Symptoms, but ambulatory. Restricted in physically strenuous activity, but ambulatory and able to carry out work of a light or sedentary nature (e.g., light housework, office work).	80	Normal activity with effort; some signs or symptoms of disease.
		70	Cares for self, unable to carry on normal activity or to do active work.
2	In bed <50% of the time. Ambulatory and capable of all self-care, but unable to carry out any work activities. Up and about more than 50% of waking hours.	60	Requires occasional assistance, but is able to care for most of his/her needs.
		50	Requires considerable assistance and frequent medical care.
3	In bed >50% of the time. Capable of only limited self-care, confined to bed or chair more than 50% of waking hours.	40	Disabled, requires special care and assistance.
		30	Severely disabled, hospitalization indicated. Death not imminent.
4	100% bedridden. Completely disabled. Cannot carry on any self-care. Totally confined to bed or chair.	20	Very sick, hospitalization indicated. Death not imminent.
		10	Moribund, fatal processes progressing rapidly.
5	Dead.	0	Dead.

Appendix B: PPI Patient Diary

Baseline	Day - 7	Day - 6	Day - 5	Day - 4	Day - 3	Day - 2	Day - 1

Complete a minimum of 7 days preceding Cycle 1, Day 1 dosing

Cycle #	Day 1	Day 2	Day 3	Day 4	Day 5	Day 6	Day 7

Cycle #	Day 8	Day 9	Day 10	Day 11	Day 12	Day 13	Day 14

Cycle #	Day 15	Day 16	Day 17	Day 18	Day 19	Day 20	Day 21

(choose only 1 score each day; do not report a range)

- | | |
|-------------------|------------------|
| 0 – no pain; | 3 – distressing |
| 1 – mild; | 4 – horrible |
| 2 – discomforting | 5 – excruciating |

Appendix C: Analgesic intake

	In the last 3 weeks, your use of pain meds has: (check one)*
Cycle 1 Day 1*	 Increased  Decreased  Remained the same
Cycle 2 Day 1	 Increased  Decreased  Remained the same
Cycle 3 Day 1	 Increased  Decreased  Remained the same
Cycle 4 Day 1	 Increased  Decreased  Remained the same
Cycle 5 Day 1	 Increased  Decreased  Remained the same
Cycle 6 Day 1	 Increased  Decreased  Remained the same
Cycle 7 Day 1	 Increased  Decreased  Remained the same
Cycle 8 Day 1	 Increased  Decreased  Remained the same
Cycle 9 Day 1	 Increased  Decreased  Remained the same
Cycle 10 Day 1	 Increased  Decreased  Remained the same
Cycle 11 Day 1	 Increased  Decreased  Remained the same
Cycle 12 Day 1	 Increased  Decreased  Remained the same
End of	 Increased

trial therapy	 Decreased  Remained the same
Follow-up	 Increased  Decreased  Remained the same

* For cycle 1 day 1, note analgesic intake over prior 1 week; for other time points, note for prior 3 weeks (or entire cycle if longer than 3 weeks)

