Premedication administered ~30 minutes before each carfilzomib infusion is ondansetron (or equivalent) IV/PO, dexamethasone (4 mg IV/PO with carfilzomib 20 mg/m² and 8 mg IV/PO with 56 mg/m²) and acetaminophen 650 mg orally (to prevent infusion reactions). Dexamethasone may be discontinued from the second cycle if the patient is tolerating carfilzomib (per investigator discretion). Normal saline (NS) 250 ml IV is administered as pre-hydration over 30 minutes. After the first cycle, pre-hydration may be discontinued at the discretion of the investigator. Carfilzomib for injection is provided as a sterile, frozen liquid formulation containing 2 mg/mL of drug.

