- Thrombocytopenia has been transient and typically resolves during the week between treatments. For platelet counts $\leq 25,000/\text{mm}^3$, carfilzomib dosing must be held. If platelet counts do not recover, the dose of carfilzomib may be reduced or held according to the Dose Reductions / Adjustments rules outlined in this protocol.
- Subjects should have anemia corrected in accordance with the Institutional guidelines.
- Carfilzomib treatment can cause nausea, vomiting, diarrhea, or constipation sometimes requiring the use of anti-emetics or anti-diarrheals. Fluid and electrolyte replacement should be administered to prevent dehydration.

Concomitant Medications

Concomitant medication is defined as any prescription or over-the-counter preparation including vitamins and supplements. Concomitant medications should be recorded from 14 days before Day 1 through the end of the subject's study participation. Any change in concomitant medications must be recorded.

Required Concomitant Medications

Female subjects of child-bearing potential must agree to use dual methods of contraception for the duration of the study. Male subjects must agree to use a barrier method of contraception for the duration of the study if sexually active with a female of child-bearing potential. Dexamethasone 4 mg PO/IV will be administered prior to all carfilzomib doses during the first cycle and prior to all carfilzomib doses during the first dose-escalation cycle. If treatment-related fever, rigors, chills, and/or dyspnea are observed post any dose of carfilzomib after dexamethasone has been discontinued, dexamethasone (4 mg PO/IV) should be re-started and administered prior to subsequent doses. Subjects should receive acyclovir or similar (famciclovir, valacyclovir) anti-varicella (anti-herpes) agent prophylaxis.

Optional and Allowed Concomitant Medications

Allopurinol (in subjects at risk for tumor lysis) is optional and will be prescribed at the Investigator's discretion. These subjects may receive allopurinol 300 mg PO BID (Cycle 1 Day -2, Day -1), continuing for 2 days after Cycle 1 Day 1 (total of 4 days), then reduce dose to 300 mg PO QD, continuing through Day 17 of Cycles.

Subjects may receive RBC or platelet transfusions if clinically indicated in accordance with institutional guidelines. Subjects who require repeated platelet transfusion support

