Modest activity is considered clinically meaningful in this relatively heavily pretreated population with metastatic CRPC that has received abiraterone acetate and/or enzalutamide (prior chemotherapy and sipuleucel-T are allowed). The null hypothesis for this trial is that the primary endpoint of 6-month PFS <10% is not clinically meaningful and the alternative hypothesis is that the true clinical PFS of interest is $\geq 30\%$. Since we will follow all subjects for at least 6 months or until progression or death, we will not have censoring and 6 months PFS can be treated as a binomial random variable. With twenty five evaluable patients we will have 80% power for an exact binomial test at the one sided 0.05 significance level of the null hypothesis that the 6-month PFS rate is 10% if the actual rate is 30%. That null hypothesis will be rejected if 6 or more of the 25 subjects survive for 6 months progression free. Twenty-eight subjects will be accrued to allow for 10% inevaluable patients.

Sample Size/Accrual Rate

A total of 28 patients will be enrolled for this trial. Accrual period will be 6 to 12 months.

Analysis of Secondary Endpoints

The Kaplan-Meier method will be used to estimate PFS and OS rates over time with standard errors estimated using Greenwood's formula. Medians and their 95% confidence intervals will also be estimated. PSA response, PSA decline $\geq 30\%$ within 3 months, RECIST responses and regressions, pain response and CTC alterations will be analyzed as secondary endpoints. CTC changes will include changes from unfavorable ($\leq 5/7.5\text{ml}$) to favorable, and declines by $>30\%$. Pain response is defined as decline in present pain index ≥ 2 points and/or decrease in analgesics. Linear regression with PSA as the dependent variable and time as the dependent variable will be performed and used to estimate PSA DT. The association of baseline whole blood 20S proteasome level with PFS and other secondary endpoints will be examined using Cox regression to generate hypotheses for selecting suitable patients for further study.

Reporting and Exclusions

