Pain response and progression

Patients with a PPI score of at least 2, or need for analgesics, or both at baseline are assessed for the pain response. A pain response is defined as a two-point reduction in the PPI score from baseline without an increase in the analgesic use or as a reduction in analgesic use without an increase in the PPI score. Pain progression is defined as an increase in the PPI score of at least one point from the nadir, an increase in analgesic use, or a requirement for palliative radiotherapy.

Progression-Free Survival

PFS is defined as the duration of time from start of treatment to time of progression or death, whichever comes first.

12. **CORRELATIVE STUDIES**

Circulating Tumor Cell (CTC) enumeration will be used as a secondary marker for efficacy of response to the treatment. Baseline CTC will be obtained prior to initiation of therapy and day 1 of cycles 2 and 4. Baseline whole blood 20S proteasome activity will also be determined.

CTC enumeration

The CELLSEARCH[®] System led to the first standardized, FDA-cleared semi-automated system that detects and enumerates CTCs of epithelial origin (CD45-, EpCAM+, and cytokeratins 8, 18+, and/or 19+) from a 7.5-mL blood sample with high sensitivity and specificity. The CELLSEARCH[®] System uses unique immunomagnetic and fluorescence imaging technology to provide rapid and reproducible analysis of CTCs with a simple 3-step process: sample collection, sample preparation, and sample analysis. System components include:

- Proprietary CellSave Preservative sample tubes
- CELLSEARCH[®] CTC Test and Control kits
- Automated CELLTRACKS[®] AUTOPREP[®] System
- CELLTRACKS ANALYZER II[®]

CellSave Preservative tubes provide an optimized cell preservative that stabilizes CTCs for up to 96 hours at room temperature, which allows shipment of samples to remote locations for analysis and improves the reproducibility and reliability of CTC analysis. CTCs are fragile and tend to degrade within a few hours when collected in standard evacuated blood collection tubes.

Once the blood sample is collected for UAB patients, the tube will be delivered to UAB main laboratory to be sent out to Quest Diagnostics for CTC enumeration. For outside sites, the tube will be sent directly to Quest Diagnostics for CTC enumeration.

Whole Blood 20S Proteasome Activity

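### Appendix C records only a self-rated recent change in analgesic use, so it cannot supply baseline analgesic need and leaves the analgesic part of pain progression open to false events

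*Combined protocol and SAP*

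**What the plan says.** The synopsis and Section 3.1 state that analgesic intake is recorded on day 1 of every cycle using Appendix C. The study calendar shows the same three-level rating. The form asks "In the last 3 weeks, your use of pain meds has" increased, decreased or remained the same. Its footnote reads "For cycle 1 day 1, note analgesic intake over prior 1 week; for other time points, note for prior 3 weeks", and goes on to allow the entire cycle where that is longer than 3 weeks.

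The rating bears on two endpoints.

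- **Pain response (secondary).** Section 11 sets the denominator: "Patients with a PPI score of at least 2, or need for analgesics, or both at baseline are assessed for the pain response".
- **Pain progression (part of the primary endpoint).** The synopsis and Section 3.1 list a greater need for analgesics under worsening pain. Section 11 makes greater analgesic use sufficient by itself and gives no amount, duration or confirmation. Sections 6.3 and 10 instead leave worsening of pain to the investigator's judgment and do not mention analgesics.

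Section 6.1 has every infusion preceded by "acetaminophen 650 mg orally (to prevent infusion reactions"), six times per cycle. Section 7 also wants acetaminophen at hand for first-dose reactions.

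There is a second source. Section 7 has concomitant medications recorded from 14 days before Day 1 and adds "Any change in concomitant medications must be recorded". Section 6.2 asks the case report form to capture all concurrent drugs, over-the-counter ones included.

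**The concern.** The form measures change within a recent window, while the endpoints need a level at baseline and a change from a stated reference. A patient taking nothing and a patient on a steady opioid dose both answer that use stayed the same. A patient whose use falls in one cycle and returns to its baseline level in the next can truthfully report an increase without ever exceeding baseline. The question is also not limited to analgesics taken for cancer pain, although the protocol itself adds acetaminophen from cycle 1 on.

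At stake are the denominator of the pain-response rate and, where an analgesic increase counts as progression, the primary endpoint. A patient who is truly progression-free at 6 months but was logged as progressed counts as a failure in a test that needs 6 successes among 25.

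**Working it through.** **What the form can and cannot supply**

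- *Baseline need.* There is no field for drug, dose, frequency or current use, so the analgesic part of the Section 11 denominator cannot be read from the form. The other part, a PPI score of at least 2, comes from the baseline diary in Appendix B.
- *Reference point.* Section 11 measures a PPI increase from the nadir but gives no reference for an analgesic increase. The form compares only with the recent past.
- *Windows.* The window is 1 week at cycle 1 day 1. At later visits it is 3 weeks by the printed question and, because every cycle is 28 days, the whole cycle by the footnote.
- *Premedication.* None is scheduled in the week before cycle 1 day 1. By cycle 2 day 1, the whole-cycle window holds 6 × 650 mg = 3,900 mg. A 3-week window (days 8 to 28) holds the doses of days 8, 9, 15 and 16: 4 × 650 mg = 2,600 mg. Scheduled exposure then repeats each cycle, so a spurious increase from this cause is most plausible once, at cycle 2.

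**The stated design (Section 10)**

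Inputs: "With twenty five evaluable patients we will have 80% power for an exact binomial test at the one sided 0.05 significance level", for a null rate of 10% against 30%, with the rule "That null hypothesis will be rejected if 6 or more of the 25 subjects survive for 6 months progression free".

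- Type I error = P(X ≥ 6 | n = 25, p = 0.10) = 0.0334
- Power = P(X ≥ 6 | n = 25, p = 0.30) = 0.8065

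The stated 80% power reproduces. A cut-off of 5 would give a type I error of 0.098, so 6 is the right cut-off.

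**Illustrative effect of false increases**

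Let f be the share of truly progression-free patients wrongly counted as progressed. The observable rate is p(1 − f). For a false-increase probability q at each of k independent visits, f = 1 − (1 − q)^k. Six visits means day 1 of cycles 2 to 7. All values of q are assumptions, and the calculation takes each false increase to be counted as an event.

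| Assumed q and k | f | Observed rate if truth is 30% | Power | Type I error |
|---|---|---|---|---|
| None | 0 | 30.0% | 80.7% | 3.3% |
| 5%, once at cycle 2 | 5.0% | 28.5% | 75.9% | 2.7% |
| 10%, once at cycle 2 | 10.0% | 27.0% | 70.4% | 2.1% |
| 1%, six visits | 5.9% | 28.2% | 75.0% | 2.6% |

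For example, 1 − 0.99^6 = 0.0585 and 0.30 × 0.9415 = 0.2824, so P(X ≥ 6 | 25, 0.2824) = 0.750. Both error columns fall in the conservative direction: power is lost, and type I error does not rise.

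**The case against.** Several stronger readings are tempting, and the documents do not carry them.

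- *That one tick ends PFS and treatment.* Section 6.3, which governs stopping therapy, and Section 10, the statistical section, leave worsening of pain to the investigator. No section turns an Appendix C answer into an event by itself, and nothing stops the investigator from discounting premedication. The exposure exists only under the synopsis, Section 3.1 and Section 11 wording.
- *That the pain-response rate cannot be computed.* The medication record starts before treatment and covers over-the-counter drugs, and the diary supplies baseline PPI. The denominator is lost only if Appendix C is the sole source.
- *That acetaminophen does contaminate the endpoint.* It is given about 30 minutes before an infusion to prevent reactions, and patients may not think of it as pain medication. The milligram totals show exposure, not misreporting.
- *That power falls to about 48%.* This needs a 5% false-increase rate compounded independently over six visits (f = 1 − 0.95^6 = 0.265, observed rate 22.1%, power 48.4%). Premedication is the same in every cycle, so it does not suggest six fresh chances. Compounding needs recurring unrelated causes, for which the documents give no rate.

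The window argument can also be pressed too far. The printed question carries the footnote's asterisk. If the footnote governs, all on-treatment cycle visits share one 28-day window, and the odd one out, cycle 1 day 1, precedes treatment and cannot be a PFS event.

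These points limit the consequences but leave the gap. The form still has no level or baseline comparison, its question and footnote still give different periods, and premedication is not excluded. No section names the medication record as the source for either pain endpoint or defines an increase.

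**Conclusion.** The concern holds as a defect of measurement and derivation. Appendix C alone cannot identify patients with baseline analgesic need. Where an analgesic increase counts as progression, the primary endpoint is open to false events.

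The sample-size calculation is correct. The size of any loss is unknown: under the assumed rates tabulated above, power would be 70% to 76% instead of 80.7%. These figures assume that each false report is counted as an event, that it falls on a patient otherwise progression-free at 6 months, and, for the six-visit case, that visits are independent. If the investigator-judgment wording governs and reports are checked against the medication record, the loss could be close to nil. The plan does not say which applies, and that conflict has to be settled first.

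**What to change.** For endpoint derivation:

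1. Name the concomitant-medication record as the source of baseline analgesic need and of change in use. Make sure its case report form page has drug, dose, frequency and indication; the protocol does not specify dose or indication now.
2. State the reference and compare equal windows, for example the 7 days before each Day 1 with the 7 days before cycle 1 day 1. In a 28-day cycle those are days 22 to 28, after the last scheduled infusion on day 16, so no scheduled premedication falls inside. State what amount counts as an increase.
3. State that protocol premedication and drugs given for infusion reactions are not counted.
4. Reword Appendix C to match, with one look-back period, and treat it as supportive data only.
5. Reconcile the pain-progression wording in the synopsis, Section 3.1 and Section 11 with that in Sections 6.3 and 10. Progression also ends therapy, so which rule should govern stopping treatment is left to the sponsor.

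The cost is a revised form and medication page, somewhat more data entry (mainly for as-needed use) and light programming. The sample size, cut-off and test are unchanged.
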